8.2.2. Parasite Clearance

We will additionally perform secondary analyses to assess the relationship between measures of DHA exposure, again including AUC_{0-12} , C_{\max} , $t_{1/2}$ and T_{\max} , and measures of parasitemia clearance. The outcome response variables for these analyses are measures of parasite clearance calculated from parasite density, as measured by thick blood smear, including parasite clearance half-life (PCT_{50}), total parasite clearance by Day 2, and time to 90% reduction in parasitemia (PCT_{90}).

PCT_{50} and PCT_{90} will be estimated using the WWARN PCE algorithm [\[4\]](#). PCT_{50} is the time from first on-study dose needed for parasitemia to be reduced by half during the log-linear phase of parasite clearance, and can be calculated by $PCT_{50} = \log_e(2)/K$, where K is the first-order clearance rate constant. PCT_{90} is the time from first on-study dose needed for parasitemia to be reduced by 90% during the log-linear phase of parasite clearance, and can be calculated by $PCT_{90} = \log_e(10)/K$. The first-order clearance rate constant K is typically equal to the negative slope of the log-parasitemia-time linear relationship during the log-linear phase of parasite clearance.

PCT₅₀ and PCT₉₀ will be estimated using the parasite density per μL . The parasite density per μL will be calculated using the formula: Number of parasites per 200 WBCs \times 40 = asexual parasites / μL . The clearance rate constant K will be calculated using the following steps according to the WWARN PCE algorithm [4] for each participant separately.

1. Perform data cleaning. Data cleaning will proceed in order as follows:
 - a. Removal of data from recurrences of parasitemia including any measurements after 7 days, measurements after a time when 2 measurements are >24 h apart, and data after the last measured zero parasitemia if the positive measurements before and after this measurement are separated by >24 h are removed.
 - b. Removal of all trailing zeros after the last nonzero parasitemia except the first zero.
 - c. Removal of repeated parasitemia measurements $<100/\mu\text{L}$ and data that fall between them.
 - d. Replacement of the first zero parasitemia measurement directly after the last positive parasitemia with the limit of detection ($40/\mu\text{L}$ [4]).
 - e. Removal of extreme values outside of the range ($0, 3 \times 10^6$) or measurements with times below zero.
 - f. Removal of outliers based on the normalized slope between each set of neighboring measurements, calculated by dividing the rate of change between each set of 2 consecutive measurements by the average rate of change over the whole profile, according to the following rules:
 - i. Remove data points in the first 12 hours associated with the condition: $\text{NormSlope}_i < -20$ and $\text{NormSlope}_{i+1} > 10$, where NormSlope_i denotes the normalized slope between the i^{th} and $(i+1)^{\text{th}}$ data points.
 - ii. Remove data points after the first 12 hours associated with either condition: $\text{NormSlope}_i < -7.5$ and $\text{NormSlope}_{i+1} > 10$, or $\text{NormSlope}_i < -40$ and $\text{NormSlope}_{i+1} > 3.75$.
 - iii. Remove any data points at any time that are associated with any of the following 4 conditions: $\text{NormSlope}_i > 2$ and $\text{NormSlope}_{i+1} < -10$, $\text{NormSlope}_i > 10$ and $\text{NormSlope}_{i+1} < -2$, $\text{NormSlope}_i > 1$ and $\text{NormSlope}_{i+1} < -20$, or $\text{NormSlope}_i > 50$ and $\text{NormSlope}_{i+1} < 0.4$.
 - iv. Remove the last parasitemia measurement if the penultimate parasitemia measurement is <200 and the last is >3 times the penultimate measurement and >100 .
2. Perform checks to determine whether the clearance rate constant cannot be estimated:
 - a. The number of nonzero parasitemia measurements (including a zero replaced by the detection limit) < 3
 - b. Initial parasitemia <1000 parasites/ μL .
 - c. Final parasitemia ≥ 1000 parasites/ μL .
 - d. Zero parasitemia measurement is recorded, but the last nonzero parasitemia ≥ 1000 parasites/ μL and the normal linear regression fitted to all datapoints excluding the zero yields a CI for the time that parasitemia is below the limit of detection includes the timepoint for when the zero was recorded.

3. Perform checks to determine if there are not enough data to estimate a lag phase.
 - a. There are <3 measurements or there is a time difference of >14 h between measurements in the first 24 h
4. Perform model fitting.

Models that will be considered include linear, quadratic, or cubic tobit or normal regression for the log-parasitemia of the form:

[figure not shown]
$$\text{Linear: } \log(P_i|t_i) = \beta_0 + t_i\beta_1 + e_i$$

$$\text{Quadratic: } \log(P_i|t_i) = \beta_0 + t_i\beta_1 + t_i^2\beta_2 + e_i$$

$$\text{Cubic: } \log(P_i|t_i) = \beta_0 + t_i\beta_1 + t_i^2\beta_2 + t_i^3\beta_3 + e_i,$$

where P_i is the participant's parasitemia at the i th time, t_i is the i th time, and e_i is the measurement error term for the i th measurement.

a. If none of the conditions in Steps 2 or 3 are met, then fit models to the natural log-parasitemia versus time data as described in the following figure provided in [4].

b. If none of the criteria in Step 2 are met but the criteria in Step 3 is met, fit tobit linear regression if a zero parasitemia measurement has been recorded for the participant or normal linear regression otherwise.

c. If any of the criteria in Step 2 are met, K and the duration of the lag phase (t_{lag}) cannot be estimated, so proceed to Step 6 below.

5. Estimate K and t_{lag} according to the following figure given in [4].

Step 1: Find Best model

Best model is defined as the model with the smallest AIC or $\text{RSS}_{\text{shared}}$ among fitted models, where appropriate.

Step 2: Identify possibly convex models

[figure not shown]
Possibly convex models are quadratic or cubic models with negative concavity somewhere over the time domain.

Step 3: If model is NOT possibly convex:

$K = -b_1$; $t_{\text{lag}} = 0$; GO TO **Step 5**

Step 4: If model is possibly convex

- 4.1 For each log-parasitaemia predicted by the Best model y_i (but excluding any measured zero parasitaemias), calculate slope S_i between this point and the preceding predicted value
- 4.2 Find the most negative slope, S_{max}
- 4.3 Calculate normalised slopes $S_n = S / S_{\text{max}}$
- 4.4 Find clearance rate constant using the chart below

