Thick and thin blood smears will be performed for quantification of *P. falciparum* parasitemia. Thick blood smears will be used for diagnosis and thin blood smears for typing the species of malaria parasites. Thick and thin blood smears for malaria diagnosis will be stained with Giemsa stain and read at 100X power light microscope. Parasites will be quantitated by counting the number of asexual *P. falciparum* parasites per 200 WBC using the patient's WBC count per μ L of blood. Samples for malaria diagnostics will be collected according to the following schedule post-first on-study dose of IV artesunate in hours: 0 (0-2 hour acceptable window), 6 (4-8 hour acceptable window), 12 (10-14 hour acceptable window), 24 (22-26 hour acceptable window), 36 (34-38 hour acceptable window) and 48 (46-50 hour acceptable window), and then parasitemia should be measured at least every 24 hours through Study Day 5 and until clearance. Measures of parasite clearance will be calculated from quantified parasite density.

Total parasite clearance is defined as having a thick blood smear that is negative for *P. falciparum*, i.e. a thick blood smear for which there are no detectable *P. falciparum* parasites per 200 WBC. The date and time of total parasite clearance will be defined as the collection date and time of the first thick blood smear to meet the definition of parasite clearance. Total parasite clearance by Day 2 will be defined as the indicator of whether total parasite clearance occurred within the first 50 hours post-first dose of IV artesunate. Further details of how total parasite clearance by Day 2 is determined are given in Section [8.2.2](#).

Additionally, parasite clearance half-life (PCT₅₀) and time to 90% reduction in parasitemia (PCT₉₀) will be estimated using the WorldWide Antimalarial Resistance Network (WWARN) parasite clearance estimator (PCE) algorithm [\[4\]](#). Details of how PCT₅₀ and PCT₉₀ are calculated are given in Section [8.2.2](#).

Additional variables that will be used in exploratory PD analyses will be defined in an addendum(s) to this SAP.

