**Step 5: END**

6. End.

PCT_{50} and PCT_{90} for each participant will then be estimated using the formulas described previously in this section. Individual estimates of K and t_{lag} will be presented in [Listing 15](#). The following pseudocode will be used to fit cubic normal and tobit regression models and to calculate model-predicted values for each participant's log-parasite density data.

```

/* Cubic Regression with Predicted Values by Participant ID */
data clearance; set clearance;
time2=time**2; time3=time**3;
log_density=log(density);
run;
proc reg data=clearance;
model log_density=time time2 time3 / p;
  
```

```

by partid;
ods output OutputStatistics=predicted;
run;

/* Cubic Tobit Regression with Predicted Values by Participant ID */
data clearance; set clearance;
time2=time**2; time3=time**3;
log_density=log(density);
/*replace parasite density values = the lower limit for the variable with.*/
if density=LOD then lower=.;
else lower=log_density;
run;
proc lifereg data=clearance outest=OUTEST(keep=partid _scale_);
  model (lower, log_density) = time time2 time3 / d=normal;
  by partid;
  /*output mean of uncensored variable*/
  output out=OUT xbeta=Xbeta;
run;
data predict; merge out outest; by partid;
  lambda = pdf('NORMAL',Xbeta/_scale_);
  / cdf('NORMAL',Xbeta/_scale_);
  /*calculate mean of censored variable*/
  predict = cdf('NORMAL', Xbeta/_scale_)
    * (Xbeta + _scale_*lambda);
run;

```

Total parasite clearance by Day 2 will be a binary variable indicating whether total parasite clearance has occurred within the first 50 hours post-first dose of IV artesunate. Total parasite clearance will be determined using all thick blood smears collected within the 50 hours from the first dose of IV artesunate. Total parasite clearance by Day 2 will be determined for participants in the PD Analysis Population with any results of thick blood smears available within 50 hours after the first dose of IV artesunate.

The relationship between AUC_{0-12} , C_{max} , $t_{1/2}$ and T_{max} , and the time-to-event response variables of PCT_{50} and PCT_{90} will be analyzed using Cox proportional hazards regression. One Cox proportional hazards regression model will be fit for each response variable and DHA exposure parameter. Covariates in these models will include the appropriate exposure parameter as well as a subset of the covariates given in Section 6.4.

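### SAP 8.2.2 fixes the white cell count at 8,000/µL when deriving PCT50 and PCT90, against the own-count rule in SAP 4.5.1 and Protocol 8.3.1, so a count that changes during clearance shifts K

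*SAP*

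**What the plan says.** Two density rules stand in the same SAP.

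- **SAP 8.2.2** governs the input to the clearance algorithm. Density is "calculated using the formula: Number of parasites per 200 WBCs" times 40; the formula ends "40 = asexual parasites" per µL. It applies to all participants and times.
- **SAP 4.5.1** counts "parasites per 200 WBC using the patient's WBC count per" µL, and adds that the clearance measures come from the density so quantified. **Protocol 8.3.1** gives the same own-count rule.

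The rest of SAP 8.2.2 depends on that density. K is "typically equal to the negative slope of the log-parasitemia-time linear relationship", with PCT50 = ln 2/K and PCT90 = ln 10/K. Cleaning calls for "Replacement of the first zero parasitemia measurement directly after the last positive parasitemia with the limit of detection", set at 40/µL. Other cleaning steps use 100 and 200/µL. K is not estimated if, among other conditions, "Initial parasitemia <1000 parasites"/µL applies or the final value is at least 1,000/µL. The tobit pseudocode identifies censored values with "if density=LOD then lower" set to missing.

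SAP section 15 lists departures from the protocol and does not mention the multiplier. The precedence clause in Protocol 11.3 covers differences between that section and the SAP. It does not reach Protocol 8.3.1 and cannot settle a conflict inside the SAP.

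**The concern.** Two programmers following the SAP could derive different K values from the same smears. The fixed multiplier is also avoidable: haematology, including WBC, is scheduled at screening, on Day 1 and daily to Day 7 (Protocol 8.1, SAP Table 2), which spans the smear schedule.

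A fixed multiplier drops out of a log slope only while the child's true WBC stays constant. If WBC moves as the illness resolves, part of the apparent fall or persistence of parasites is really white cell movement. That enters K, and through K two of the three parasite-clearance measures.

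The planned output would not reveal it. Table 23 and Listing 14 show parasites per 200 WBC, so own-count density never appears.

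**Working it through.** **Inputs from the documents:** multiplier 40; limit of detection 40/µL; cut-offs 100, 200 and 1,000/µL; K as a log-density slope; smears at 0, 6, 12, 24, 36 and 48 h.
**Assumed, because the documents give none:** WBC levels and trends, and true half-lives of 2, 3 and 5 h.

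**1. The plan's own figure.** 40 × 200 = 8,000 WBC/µL. One parasite × 40 = 40/µL, which is the stated limit. The multiplier and the limit agree with each other.

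**2. Effect on K.** Let N be the count per 200 WBC. Own-count density is D = N × WBC/200, so the fixed-multiplier density is N × 40 = D × 8,000/WBC. Taking logs and slopes:

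K(fixed) = K(own) + d ln(WBC)/dt.

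This is exact for a log-linear fit with ln(WBC) linear in time.

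**3. Constant WBC.** The added term is zero. Log-linear fits at 0, 6, 12 and 24 h with WBC held at 4,000, 8,000, 12,000 or 16,000 gave K = 0.23105/h under both rules at a 3 h half-life. Tobit fits with a final zero at 36 h also agreed under both rules (0.2452/h at WBC 4,000; 0.2444/h at 12,000 and 16,000), provided the own-count limit is WBC/200.

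**4. WBC halving over 48 h.** The change in K is −ln 2/48 = −0.0144/h. Relative to K = ln 2/half-life, this is half-life/48:

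| Half-life | K (/h) | Fall in K |
|---|---|---|
| 2 h | 0.3466 | 4.2% |
| 3 h | 0.2310 | 6.2% |
| 5 h | 0.1386 | 10.4% |

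**5. Changes over 24 h.** Error in PCT50 under the fixed multiplier (PCT90 moves by the same percentages):

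| WBC path | 2 h | 3 h | 5 h |
|---|---|---|---|
| 10,000 to 8,000 | +3% | +4% | +7% |
| 12,000 to 8,000 | +5% | +8% | +14% |
| 16,000 to 8,000 | +9% | +14% | +26% |
| 8,000 to 12,000 | −5% | −7% | −11% |

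**6. Cut-offs.** A cut-off c under the fixed multiplier equals an own-count density of c × WBC/8,000. The 1,000/µL rule therefore corresponds to 500, 1,500, 2,000 and 2,500/µL at WBC 4,000, 12,000, 16,000 and 20,000. At WBC 20,000, a child starting between 1,000 and 2,500/µL by own count is declared not estimable. At 4,000, a child starting at 500/µL passes. The 100 and 200/µL cleaning rules scale the same way.

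**7. Tobit tie.** Under the fixed multiplier a positive smear of one parasite equals 40/µL, so the code treats it as left-censored, like a replaced zero. Under own-count density with a limit of WBC/200, one parasite again equals the limit. The tie comes from testing for equality with the limit, not from the multiplier.

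**The case against.** The strongest reply is that the shift in K need not reach the reported result. PCT50 and PCT90 go into Cox models, whose partial likelihood uses only the ordering of times. A WBC drift common to all children adds the same constant to every K and leaves the ordering and hazard ratio unchanged. Drift that varies between children but is unrelated to DHA exposure adds noise. Systematic distortion needs drift that varies with exposure. This stands: the percentages above are errors in K and PCT50, and a reader who infers equally large bias in the hazard ratios goes beyond the documents.

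Four other inferences also fail.

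- A reader might infer that any WBC other than 8,000 biases the clearance rate. Step 3 shows that a constant one does not; it acts only through the cut-offs.
- A reader might call the cut-offs wrong. Under the fixed rule 1,000/µL is 25 counted parasites for every child, which is coherent. The cut-offs are displaced only relative to own-count density, and the documents do not show which density the cited algorithm's thresholds assumed.
- A reader might treat WBC as a severity marker. It is neither a primary response variable nor one of the SAP's severe-malaria criteria.
- A reader might treat the set of children with an estimable K as an outcome. It only determines who contributes to Table 25.

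Own-count density has a price. WBC is measured about daily and smears are 6 to 12 h apart early on, so matched values are stepwise and add some noise to log density, which feeds the slope-based outlier rules and curve selection. The early cleaning step for repeated values below 100/µL may also remove some one-parasite smears, so the frequency of the tobit tie is unknown.

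**Conclusion.** The contradiction is certain and nothing in either document resolves it. That a WBC trend during clearance enters K follows directly from the formula. Its size rests on assumed trajectories: 4% to 10% of K for a halving over 48 h, and PCT50 errors from −11% to +26% across the 24 h scenarios. The direction of any effect on the hazard ratios is not determinable from the documents.

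Total clearance by Day 2 needs only a negative smear and is untouched. The affected outcomes are secondary, unadjusted for multiplicity, in a study that describes itself as hypothesis-generating. The tobit tie is a separate coding defect that holds under either density rule. This should be corrected before analysis, but it does not threaten the primary analysis.

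**What to change.** - State one rule in SAP 4.5.1 and 8.2.2: count/200 × the child's WBC nearest in time to the smear, with 8,000 only when no WBC is available.
- Set the replaced zero to WBC/200 instead of 40/µL.
- Identify censored values by an explicit zero-smear flag instead of testing whether density equals the limit. Make this change whichever density rule is kept.
- Report the fixed-multiplier version as a sensitivity analysis, including how many children have an estimable K under each rule.

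If the sponsor prefers to keep the fixed multiplier as the main rule, it should be justified, listed in section 15 and paired with an own-count sensitivity analysis.

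The cost is SAP wording, one matched derivation, a censoring limit that varies by smear, and a second run of the algorithm. No new data are needed. The small downside is the stepwise WBC noise described above.

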7 STUDY SCHEDULE

7.1 Screening

Starting at the emergency department of the hospital, participants diagnosed by the attending physician and have received a prescription of artesunate for severe malaria will be screened for study eligibility and enrolled.

Recruitment will be progressive over a single malaria transmission season so that up to 100 children of either sex who fulfill the inclusion criteria are enrolled. Participants will be recruited by non-coercive methods among children aged 6 months-14 years residing near the study site. A parent/guardian of a child diagnosed with severe malaria will be informed of the study to determine if they are interested to have their child participate. Children who are of the age of assent (age 8 in Uganda) and above and who are conscious will also be informed of the study to determine if they are interested. Informed consent of a parent/guardian and assent for children ≥ 8 and <18 years of age who are conscious at enrollment and otherwise able to provide assent is required for enrollment. After the study has been explained to a potential participant's parent/guardian, and to a potential participant in the case of a conscious child aged 8-14 years old, they will be provided with a copy of the consent form and assent form if applicable. The consent/assent process will be conducted in a semi-private area to ensure confidentiality, to reduce the likelihood of other participants influencing their decision, and to allow further time to make a final decision. A single informed consent document, and a single assent document when applicable, will be used for screening and other study procedures. Only participants who receive a first dose of IV artesunate are considered enrolled in the study. Administration of artesunate therapy will not be delayed for enrollment procedures. Participants may still be enrolled up to 24 hours after first dose of IV artesunate. In the case of unconscious children who are the age of assent, only informed consent of a parent/guardian is required for enrollment. Once the child becomes conscious, assent will be obtained from the child to determine if their participation in the study will continue.

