All screening tests, medical history and examinations will be performed only after study consent/assent where applicable is obtained. If an individual's medical chart or results diagnostic tests performed as part of an individual's medical care are going to be used for screening, written informed consent must be obtained before review of that information.

An eligibility checklist will be prepared for each participant and will later become part of the source document for participants enrolled in the trial. A unique identification number will be assigned to each study participant. A medical history will be taken. Concomitant medications will be documented. Physical examination (including Blantyre coma score (BCS)) and laboratory

screening tests will include: hemoglobin, platelets, white blood cell (WBC) count, neutrophil count; serum lactate, bicarbonate, blood urea nitrogen (BUN), calcium, creatinine, glucose, alanine aminotransferase (ALT), aspartate aminotransferase (AST), total and direct bilirubin, sodium, and potassium; and urinalysis. Laboratory testing will be performed at the Lancet laboratory at the study site and at a local reference laboratory if needed. Results obtained within 24 hours prior to enrollment can be included as baseline labs and would satisfy both screening and enrollment/baseline labs. A thick and thin blood smear will be performed for estimation of parasite density. A dried blood spot specimen will be collected for artemisinin resistance assessment. A blood specimen will be collected in a PAXgene tube for *P. falciparum* gene expression analysis. Recruitment will continue over a single malaria transmission season until up to 100 eligible participants have fulfilled all the inclusion criteria and none of the exclusion criteria.

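### The clearance algorithm's clock starts at the first on-study dose, so it discards screening smears taken after a pre-enrollment dose and selects pre-treated children toward longer PCT50 and PCT90

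*SAP*

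**What the plan says.** **Clock.** SAP 8.2.2 says PCT50 "is the time from first on-study dose needed for parasitemia to be reduced by half" in the log-linear phase, and defines PCT90 in the same way. SAP 4.5.1 sets the smear "schedule post-first on-study dose of IV artesunate in hours: 0 (0-2 hour acceptable window"), followed by 6, 12, 24, 36 and 48 h. The notes to Tables 25 and 26 repeat the on-study origin. Step 1e does not define time zero itself, so this is the clock it inherits.

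**Deletion and estimability.** Step 1e removes "or measurements with times below zero". Step 2b lists "Initial parasitemia <1000 parasites"/µL as a reason K cannot be estimated. Under step 4c any Step 2 failure means no K, and so no PCT50 or PCT90.

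**Who is affected.** Protocol 7.1 states: "Participants may still be enrolled up to 24 hours after first dose of IV artesunate". It also plans a screening smear: "A thick and thin blood smear will be performed for estimation of parasite density". Screening tests require consent first, so in a pre-treated child this smear can fall after the first dose.

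**Other clock.** The SAP uses the first dose, on study or not, for dosing times (4.1), baseline (3.3) and total clearance by Day 2 (4.5.1, 8.2.2).

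**The concern.** In a child first dosed on study, smears at negative times precede drug action and removing them is sensible. In a pre-treated child, smears between the first dose and the first on-study dose belong to the clearance curve. Deleting them can remove the only high count in the profile.

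The child then fails step 2b because parasites fell quickly, so entry to the analysis depends on the outcome. Adjusting for prior therapy, a candidate covariate in SAP 6.4, does not correct that. The planned no-prior-therapy sensitivity analysis removes these children but leaves the main result as it is. The problem would also be hard to see: Table 25 gives only N and N*, and Listing 15 only K and the lag time. Neither shows which Step 2 rule failed or in whom.

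**Working it through.** The plan states no figure for the share of pre-treated children or the share with an estimable K, so there is nothing to reproduce. Density is count per 200 WBC × 40, so the 1000/µL threshold is 25 parasites and one parasite is 40/µL, which matches the stated detection limit.

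**Illustrative record.** First dose 06:00; screening smear 08:00, 60,000/µL; first on-study dose 18:00; 0-h smear 18:30, 800/µL; then a lower positive count, then zero.
- On-study clock: the 08:00 smear is at −10 h and is deleted. The profile starts at 800, below 1000, so step 2b fails and there is no PCT50 or PCT90.
- First-dose clock: the profile starts at 60,000 at 2 h, has at least three usable points and ends low, so K is estimable.

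**Break-even density.** With T hours from first dose to first on-study dose and half-life h, log-linear decline gives D(T) = D0 × 2^(−T/h). The child passes step 2b without the earlier smear only if D0 ≥ 1000 × 2^(T/h). Doses are planned at 0, 12 and 24 h from the first dose, so T is typically near 12 or 24 h.

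| h (hours) | T = 12 h | T = 24 h |
|---|---|---|
| 2 | 64,000 | 4.1 million |
| 2.5 | 27,858 | 776,047 |
| 3 | 16,000 | 256,000 |
| 4 | 8,000 | 64,000 |

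The hurdle rises steeply as h shortens. That is the selection.

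**Simulated effect of the deletion.** Assumptions, none from the documents: density at first dose lognormal, median 10,000 to 100,000/µL, log-SD 1.5; half-life median 2 to 3 h, log-SD 0.35; lag 0 or 4 h; one screening smear, uniform between first dose and first on-study dose. Steps 1a, 1c, 1f and 2d were not simulated.

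| | T = 12 h | T = 24 h |
|---|---|---|
| Estimable as written, full range | 14–92% | 1–44% |
| Estimable with smear kept, full range | 49–99% | 11–82% |
| Central case (30,000/µL, 2.5 h, no lag), as written → kept | 42% → 79% | 8% → 38% |
| Central case, excess of retained children's median true half-life over all such children | 22% → 6% | 56% → 26% |

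A separate run with half-life log-SD 0.3 gave 49% (12 h) and 7% (24 h) estimable as written in the central case.

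**Sensitivity to screening time.** With uniform screening, keeping the smear adds 8–43 points of estimability at 12 h and 12–44 at 24 h. If screening falls in the last 2 h before the on-study dose, it adds 5–18 and 1–8 points.

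**The case against.** **The schedule is the deeper cause.** The planned series starts at the first on-study dose, after earlier drug effect, and among scheduled smears step 1e can normally reach only the screening smear. This stands in part. Even with the smear kept, the central case at 24 h has 38% estimable and a 26% excess half-life. But in the same case the deletion accounts for the move from 38% down to 8%.

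**A reader might infer that most pre-treated children are lost and only slow clearers remain.** The documents do not support that. With half-lives of 1.5 to 5 h and no lag, the share below 1000/µL ran from 4% to 95% at 12 h and from 27% to 100% at 24 h. At 30,000/µL and 2.5 h, 31% of estimable children at 12 h still cleared faster than the median child, against 1% at 24 h.

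**K is a slope, so the origin might seem not to matter otherwise.** It does. Steps 1f-i and 1f-ii switch at 12 h and step 3a looks at the first 24 h. On a first-dose clock, a child whose on-study dose is at 24 h will usually have too few smears in that window and gets a linear fit without lag estimation.

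**Exposure alignment.** AUC0-12 and Cmax belong to the first on-study dose, so earlier smears show clearance before the measured exposure. This is true but minor: nearly all clearance in these children already follows an earlier, unmeasured dose.

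**Existing safeguards.** The no-prior-therapy analysis is free of this mechanism, Day 2 clearance needs no K, and these are secondary outcomes in a hypothesis-generating study. That limits the consequence, but does not repair the main Table 25 models.

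**Conclusion.** The concern holds as a selection problem among pre-treated children. On the on-study clock, steps 1e and 2b together drop faster clearers more often, which lengthens PCT50 and PCT90 in those who remain and reduces N.

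The size cannot be fixed from the documents. It depends on the share pre-treated, starting density, half-life and screening-smear timing, none of which is given. The plausible range is about 1 to over 40 percentage points of estimability among pre-treated children. The effect on the whole PD population scales with the unknown share pre-treated.

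A reader might extend the point to children first dosed on study whose zero-time smear was taken just before the dose. The planned 0-h window is 0–2 h after the dose, so that arises only if the planned smear was missed.

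**What to change.** In SAP 8.2.2, define time zero for the clearance estimator as the first IV artesunate dose, pre-enrollment or on-study, as the SAP already does for dosing times, baseline and Day 2 clearance. Keep all quantified smears from that time, and apply steps 1e and 2b on that clock. Align the PCT50/PCT90 definitions and the Table 25/26 notes. Report the number failing each Step 2 rule by prior-therapy status. Keep the on-study-clock result as a sensitivity analysis. Optionally, let a pre-dose smear stand for time 0 in a child first dosed on study who missed the 0–2 h smear.

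The cost is wording and a few lines of code. Pre-enrollment dose dates and times are already to be listed (Listing 8), and SAP 6.5 has an imputation rule for missing dosing times.

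The downsides should be stated in the SAP:
- The analysis relies on recorded or imputed pre-enrollment dose times.
- The 12-h and 24-h windows in steps 1f and 3a shift, so some pre-treated children get a linear fit with no lag estimate.
- Part of the curve precedes the dose whose AUC and Cmax are measured.
- Some schedule-driven selection remains, which the failure counts would make visible.
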